- Subjects with prior treatment for PCa including BT, RT or hormone therapy.

c) Number of Subjects:

This is a 3+3 dose escalation design study to determine the MTD. This study will use 2 dose levels and 1-6 subjects at each dose level. The first subject enrolled at each dose level (60 and 75 Gy) will be monitored for the entire DLT window (3 months post EBRT completion) with subsequent subjects enrolled either at the same dose (if only 1 of the first 3 subsequent subjects at the given dose experiences DLT) or in the

[Type here]

Protocol Title:	A Phase I Single-Arm Open Label Dose-Escalation Study of CivaSheet with Radical Prostatectomy with or without Adjuvant External Beam Radiation Therapy in Patients with High Risk Prostate Cancer
Principal Investigator Name/Contact Info:	[name]/ [contact]/ [contact]
Primary Contact Name/Contact Info	[contact] [name]
Date Revised:	7/22/2022
Study Number:	GCO#1: 16-1314

next dose level if the preceding dose is deemed acceptable (i.e., < 33% DLT within 90 days post EBRT). If in the first subject, Grade 4-5 hematuria, fistula formation, proctitis or death occurs in the DLT window, the trial will be terminated. The total number of subjects for this single arm 3+3 trial design is therefore a minimum of 1 and a maximum of 12.

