The dose escalation design utilized for the present study will proceed as follows: The first subject will be enrolled at 60 Gy. Once the entire DLT window (i.e., 90 days post EBRT) is complete for this first subject, the next 2 subjects will be enrolled at 60 Gy. If in the first subject, grade 4 or higher hematuria, proctitis, fistula formation or death occurs in the DLT window, the trial will be terminated. If 2 of the first 3 subjects experience DLT at 60 Gy, the trial will be terminated. If 0 or 1 of the first 3 subjects enrolled at 60 Gy experience a DLT after the third subject's entire DLT window is complete, an additional three subjects will be enrolled at 60 Gy. If $\geq 33\%$ of subjects experience DLT at 60 Gy, the trial will be terminated. If after the sixth subject's DLT window is complete and < 33% of subjects experience DLT at 60 Gy, the first subject at 75 Gy will be enrolled. Once the entire DLT window (i.e., 90 days post EBRT) is complete for this first subject at 75 Gy, the next two subjects will be enrolled at 75 Gy. If in the first subject at 75 Gy, grade 4 or higher hematuria, fistula formation, proctitis or death occurs in the DLT window, 60 Gy will be considered the MTD and no additional subjects will be enrolled at 75 Gy. If 2 of the first 3 subjects experience DLT at 75 Gy, 60 Gy will be considered the MTD and no additional subjects will be enrolled at 75 Gy. If 1 or 0 of the first 3 subjects enrolled at 75 Gy experience a DLT after the third subject's entire DLT window is complete, an additional 3 subjects will be enrolled at 75 Gy. If $\geq 33\%$ of subjects experience DLT at 75 Gy, no additional subjects will be enrolled at 75 Gy and 60 Gy will be considered the MTD. If after the sixth subject's DLT window is complete and < 33% of subjects experience DLT at 75 Gy, 75 Gy will be considered the MTD.

The true risk of toxicity is expected to be in the range of 10-50%. The following table shows the corresponding probabilities of dose escalation.

True Risk of Toxicity	0.1	0.2	0.3	0.4	0.5
Probability of Escalation	0.96	0.87	0.69	0.50	0.31

[Type here]

Protocol Title:	A Phase I Single-Arm Open Label Dose-Escalation Study of CivaSheet with Radical Prostatectomy with or without Adjuvant External Beam Radiation Therapy in Patients with High Risk Prostate Cancer
Principal Investigator Name/Contact Info:	[name]/ [contact]/ [contact]
Primary Contact Name/Contact Info	[contact] [name]
Date Revised:	7/22/2022

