Study Number:	GCO#1: 16-1314

A minimum of 3 and a maximum of 6 subjects within a dose level must be observed for one cycle (90 day post EBRT completion) before accrual to the next higher dose level may begin.

Three patients within a dose level must be observed for one cycle (30 days post EBRT) before accrual to the next higher dose level may begin. The treatment for this study is RP + Civasheet implant + adjuvant EBRT for patients with high-risk or intermediate (non-clinically localized) prostate cancer with adverse pathologic features including seminal vesicle invasion, extra prostatic extension or a positive surgical margin. Since the clinical guidelines recommend adjuvant EBRT post RP only for patients with adverse pathologic features at RP, patients without these adverse pathologic features at RP will be replaced with additional patients at that dose level. Since however eligibility criteria is for high risk or non-clinically localized intermediate risk prostate cancer, the anticipated number of patients without these adverse pathologic features who will not receive adjuvant EBRT is 2 or less. While toxicities among these patients will be monitored according to the protocol, toxicities among these patients will not be used in determinations of the MTD. The MTD will only be determined for patients undergoing RP + Civasheet implant + adjuvant EBRT.

If a subject is withdrawn from the study prior to completing the entire cycle of therapy or prior to completing the entire DLT window without experiencing a DLT prior to withdrawal, an additional subject may be added to that dose level. Subjects missing doses due to a DLT will not be replaced since these subjects will be considered to have experienced a dose limiting toxicity.

d) Study Timelines:

The duration of an individual subject's participation in this study including follow-up is 5 years.

The expected duration for the investigators to complete this ranges between 1 month for a minimum of 1 subject and 44 months for a maximum of 12 subjects.

Table 1. Time and events table for those undergoing RP + Civasheet implant + adjuvant EBRT.

[Type here]

Effective Date: 10/18/2022

End Date: 10/17/2023

Protocol Title:	A Phase I Single-Arm Open Label Dose-Escalation Study of CivaSheet with Radical Prostatectomy with or without Adjuvant External Beam Radiation Therapy in Patients with High Risk Prostate Cancer									
Principal Investigator Name/Contact Info:	[name]/ [contact]/ [contact]									

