hematuria, proctitis, or fistula are not observed. If 2 additional subjects are enrolled at 60 Gy, we will review for DLTs after completion of the 90 day DLT window and enroll 3 additional subjects at 60 Gy if DLT has been observed in 1 subject, or enroll 1 subject at 75 Gy if no DLT were observed or terminate the trial if $\geq 33\%$ DLT were observed in all subjects. For the next group of subjects at 60 Gy, we will review DLT/toxicity after all three subjects have completed the 90 days DLT window after EBRT. After the first subject's DLT window is complete (90 days post-EBRT) at 75 Gy, we will make a decision to enroll additional subjects at 75 Gy only if Grade 4-5 hematuria, proctitis, or fistula are not observed. If 2 additional subjects are enrolled at 75 Gy, we will review for DLTs after completion of the 90 day DLT window and enroll 3 additional subjects at 75 Gy if DLT has been observed in 1 subject, or terminate the trial if $\geq 33\%$ DLT were observed among the first three subjects at 75 Gy. For the next group of three subjects at 75 Gy, we will review DLT/toxicity after all three subjects have completed the 90 days DLT window. We will additionally describe rates of complications and toxicity (i.e., acute and late overall, GU and GI) by grade and by dose once the 6 month follow-up period is complete for all subjects. Toxicities among those not receiving EBRT will not affect the MTD determination or the decision to enroll additional patients at the same dose or at a higher dose. The DMC will review data at least once annually.

If the DMC recommends termination of the study we will terminate the study. If in the first subject at any dose Grade 4-5 hematuria, proctitis or fistula occur, we will terminate the study. If $\geq 33\%$ of subjects experience DLT (i.e., Grade 3 hematuria, proctitis, urinary retention) within the first 90 days post EBRT, the trial will be closed.

The Clavien-dindo classification of surgical complications will be used to assess complications and the NCI-CTCAE v4.0 in addition to the RTOG acute and late morbidity scoring criteria will be used to grade adverse events and toxicity.

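### After 0 of 3 DLTs at 60 Gy the protocol gives two opposite instructions, and the SAP sets no minimum number of men at 60 Gy, so 60 Gy could be named the MTD on three men

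*Protocol*

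**What the plan says.** Three parts of the protocol and one of the SAP bear on the look after three men at 60 Gy.

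- **Protocol 3(c), escalation paragraph.** "If 0 or 1 of the first 3 subjects enrolled at 60 Gy experience a DLT", then "an additional three subjects will be enrolled at 60 Gy". The next dose opens later: after the sixth man's "DLT window is complete and < 33% of subjects experience DLT at 60 Gy, the first subject at 75 Gy will be enrolled".
- **Protocol, safety-monitoring text (before the Adverse Events heading).** Three more men are added at 60 Gy if one DLT was seen, "or enroll 1 subject at 75 Gy if no DLT were observed".
- **Protocol 3(c), other sentences.** The opening paragraph ties further enrolment at the same dose to one DLT ("if only 1 of the first 3 subsequent subjects at the given dose experiences DLT"). After the escalation table a floor is set: "A minimum of 3 and a maximum of 6 subjects within a dose level must be observed" for 90 days before the next dose opens. The sentence after it says three patients and 30 days.
- **SAP, Primary Outcome.** The trial closes if at least 33% have a DLT at 60 Gy, or if the first man there has a listed Grade 4 or higher event. If more than 33% have a DLT at a dose, the dose below is the MTD. If the first man at 75 Gy has a listed Grade 4 or higher event, 60 Gy is the MTD. No number of men at 60 Gy is required.

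Protocol 3(c) has the same consequence at the upper dose: "If 2 of the first 3 subjects experience DLT at 75 Gy, 60 Gy will be considered the MTD". It also prints a table of escalation probabilities for true risks 0.1 to 0.5: 0.96, 0.87, 0.69, 0.50, 0.31.

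**The concern.** The MTD is the primary outcome, and the most favourable result at the first full look leads to two incompatible actions: keep treating at 60 Gy, or treat at 75 Gy on three men's data. Neither document ranks the two texts.

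The SAP inherits the gap. Its clauses naming 60 Gy the MTD look only at what happens at 75 Gy. Under the 3(c) escalation paragraph this does no harm, because six men have always been treated at 60 Gy by then. Under the monitoring text, 0/3 at 60 Gy followed by failure at 75 Gy makes 60 Gy the MTD on three men, and nothing asks for more men at 60 Gy first.

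**Working it through.** **Inputs.** True DLT risks p = 0.1 to 0.5 and the printed table come from protocol 3(c). Write q = 1 - p. Men are treated as independent with equal risk within a dose. At 1/3 the trial is taken to expand. With six men, < 33% means at most 1/6, since 2/6 = 33.3%.

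**Step 1: the printed table** ("The following table shows the corresponding probabilities of dose escalation").

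- 3(c) rule (always six, stop at 2 or more of 3): q³ × P(at most 1 of next 3) + 3pq² × q³
- Monitoring rule (0/3 escalates; 1/3 needs 0 of the next 3): q³ + 3pq² × q³
- Monitoring rule with 2/6 allowed: q³ + 3pq² × P(at most 1 of next 3)
- 3(c) path with 2/6 allowed: q³ × P(at most 2 of next 3) + 3pq² × P(at most 1 of next 3)

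| True risk | 0.1 | 0.2 | 0.3 | 0.4 | 0.5 |
|---|---|---|---|---|---|
| Printed | 0.96 | 0.87 | 0.69 | 0.50 | 0.31 |
| 3(c), < 33% | 0.886 | 0.655 | 0.420 | 0.233 | 0.109 |
| Monitoring, < 33% | 0.906 | 0.709 | 0.494 | 0.309 | 0.172 |
| Monitoring, 2/6 allowed | 0.965 | 0.856 | 0.689 | 0.496 | 0.313 |
| 3(c) path, 2/6 allowed | 0.965 | 0.852 | 0.680 | 0.482 | 0.297 |

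Under < 33% neither route reproduces the table; the largest gaps are 0.27 for 3(c) and 0.20 for the monitoring rule. If 2/6 passes, both routes come within 0.02 of every cell.

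**Step 2: how often the conflicting look arises.** P(0/3) = q³ = 0.729, 0.512, 0.343, 0.216, 0.125.

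**Step 3: difference between the routes in opening 75 Gy, under < 33%.** Monitoring minus 3(c) = q³ × P(2 or more of next 3) = 0.020, 0.053, 0.074, 0.076, 0.063, or about 2, 5, 7, 8 and 6 points.

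**Step 4: chance that 60 Gy is named the MTD on three men, monitoring route, < 33%.** This is P(0/3 at 60 Gy) × P(75 Gy fails). The monitoring text is silent on 0/3 at 75 Gy, so two values are given: 75 Gy accepted at 0/3, and 75 Gy always taken to six. The documents give no risks by dose; the pairs are assumptions within 10-50%, with the 75 Gy risk at least the 60 Gy risk.

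| Risk at 60 / 75 Gy | Accepted at 0/3 | Always six |
|---|---|---|
| 0.1 / 0.1 | 0.729 × (1 - 0.906) = 0.07 | 0.729 × (1 - 0.886) = 0.08 |
| 0.1 / 0.3 | 0.37 | 0.42 |
| 0.2 / 0.3 | 0.26 | 0.30 |
| 0.2 / 0.4 | 0.512 × (1 - 0.309) = 0.35 | 0.512 × (1 - 0.233) = 0.39 |
| 0.3 / 0.5 | 0.28 | 0.31 |
| 0.1 / 0.5 | 0.729 × (1 - 0.172) = 0.60 | 0.729 × (1 - 0.109) = 0.65 |

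The range is about 7% to 65%. If 2/6 were allowed, the 0.2/0.4 figure would be about 26%. The first-man rule at 75 Gy is left out. If every first-man DLT were Grade 4 or higher, it would add at most 0.512 × 0.4 × 0.6⁵ = 0.016 at 0.2/0.4. Fistula and death are not modelled.

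**Step 5: precision.** Exact 95% intervals for the DLT rate are 0 to 71% for 0/3, 0 to 46% for 0/6, and 0.4 to 64% for 1/6.

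**The case against.** The sponsor could say the plan is an ordinary 3+3 design, so escalation on 0/3 is intended. Several texts support that: the 3+3 label, the opening paragraph of 3(c), a floor of three that would be idle if six were always needed, and a printed table slightly closer to the monitoring route. The first man at 75 Gy is also watched alone for his full 90-day window on either route, so the immediate exposure is one man. And six men prove little: 1/6 would pass, with an upper limit of 64% against 71% for 0/3.

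All of this stands as evidence about intent and risk. It does not remove the conflict, because the escalation paragraph of 3(c), which presents itself as the design in use, treats 0 and 1 DLT alike. Nor does the table decide between the routes: both fit within 0.02 once 2/6 passes, which the protocol's own limit forbids.

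A reader might also infer that the documents conflict on failure at 75 Gy, because the monitoring text and Stopping Rules end the trial while 3(c) and the SAP name 60 Gy the MTD. The documents do not support that reading. With 75 Gy the top dose, ending enrolment and reporting 60 Gy as the MTD can both be done. The wording needs only clarification.

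**Conclusion.** The contradiction after 0/3 at 60 Gy is real, and so is the missing minimum in the SAP. It affects the decision rule for the primary outcome and should be corrected.

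Its size depends on unknown risks. The conflicting look is reached with probability 73% down to 13% as the true 60 Gy risk runs from 0.1 to 0.5. The 7% to 65% chance of an MTD on three men applies only if the monitoring route is followed, and the 35-39% figure is one assumed pair, not an estimate for this trial. The 2 to 8 point difference in opening 75 Gy is modest.

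It would go too far to infer that three men will be the basis of the MTD, or that six would exclude a DLT rate of 33%. The supportable conclusion is that the plan does not say which evidence is enough.

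**What to change.** State one rule in every place.

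- **Preferred:** the 3(c) escalation paragraph, which is also the safer text. Require six evaluable men at 60 Gy through 90 days, with at most 1/6 DLT, before 75 Gy opens. Write the three-man look as a count: stop on 2 or more, expand on 0 or 1. As a percentage, 1/3 = 33.3% also meets the closure limit. Conform the opening paragraph of 3(c), the floor sentences (removing the 30-day one) and the monitoring text.
- **Alternative:** keep escalation on 0/3, but require 60 Gy to be filled to six before it is named the MTD. This closes the MTD gap but still treats men at 75 Gy on three men's data.
- **Either way, in the SAP:** 60 Gy is the MTD only with six evaluable men there and at most 1/6 DLT. Change > 33% to ≥ 33% to match the protocol.
- **Table:** print the values for the chosen rule. Section 3(c): 0.89, 0.66, 0.42, 0.23, 0.11. Monitoring rule: 0.91, 0.71, 0.49, 0.31, 0.17.
- **Clarification only:** say in the monitoring text and Stopping Rules that failure at 75 Gy stops enrolment at 75 Gy and leaves 60 Gy as the MTD, subject to the six-man condition.

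Cost of the preferred rule: wording, one table, up to three more men at 60 Gy, and 42 + 35 + 90 = 167 days (about 24 weeks) plus accrual. The chance of opening 75 Gy falls by 2 to 8 points. The maximum stays at 12 men. Six consecutive windows (1, 2 and 3 men at each dose) take 6 × 167 = 1,002 days, about 33 months, leaving about 11 of the stated 44 months for accrual.

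### One DLT in three both expands the cohort and closes the trial; Protocol sections 3(c) and 3(f) disagree at none in three; the escalation table fits neither

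*Protocol*

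**What the plan says.** **One DLT in three.** For the three-subject review at 75 Gy, the safety-monitoring text in Protocol section 3(f) says to "enroll 3 additional subjects at 75 Gy if DLT has been observed in 1 subject, or terminate the trial if" at least 33% "DLT were observed among the first three subjects at 75 Gy". Its 60 Gy sentence has the same two limbs, although its 33% refers to all subjects. The summary rule that closes this text, the Stopping Rules under Adverse Events, and (for 60 Gy) the SAP's Primary Outcome section all close the trial at 33% or more, without naming a review point.

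**None in three.** Section 3(c) treats none and one alike: "If 0 or 1 of the first 3 subjects enrolled at 60 Gy experience a DLT", then "an additional three subjects will be enrolled at 60 Gy". Section 3(f) instead separates them at 60 Gy: after one DLT it adds three men, "or enroll 1 subject at 75 Gy if no DLT were observed or terminate the trial if" the 33% limit is reached. For 75 Gy, 3(f) gives no action after none in three, while 3(c) again adds three. A later paragraph of 3(c) supports moving on after three: "A minimum of 3 and a maximum of 6 subjects within a dose level must be observed for one cycle" before the next dose opens.

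**The table.** Section 3(c) expects a true risk of 10% to 50% and states: "The following table shows the corresponding probabilities of dose escalation". The values at 0.1, 0.2, 0.3, 0.4 and 0.5 are 0.96, 0.87, 0.69, 0.50 and 0.31.

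**Two related wordings.** The opening of 3(c) keeps the same dose "if only 1 of the first 3 subsequent subjects at the given dose experiences DLT", which reads as if subject 1 were not counted, although the detailed steps count him. The SAP sets the MTD with a strict more-than-33% rule, but closes at 60 Gy with 33% or more.

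**The concern.** A 3+3 design has few possible results at each review, so every one of them needs exactly one prescribed action. Here the conflicts fall on the two results that let a dose continue. None or one DLT in three together make up 97% of first cohorts at a true risk of 0.1, and 50% at 0.5.

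At one in three, the 75 Gy sentence orders both more enrolment and termination, whether 33% is taken literally or as shorthand for one third. At none in three, the choice of section decides whether three or six men are observed at 60 Gy before the dose rises. These rules fix the MTD, which is the primary outcome. The table is the plan's only statement of how the design behaves, so an error in it misinforms anyone judging how readily the trial would escalate.

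**Working it through.** **Inputs.** True DLT risk p = 0.1 to 0.5 and the printed probabilities, both from the table in 3(c); q = 1 − p. Subjects are taken as independent and evaluable, with constant risk. The stop for a Grade 4 or higher event in the first subject is set aside until step 5.

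**1. Trying to reproduce the table.**

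- *3(c) rule.* At most 1 of 3, then under 33% of six. Since 1/6 = 16.7% passes and 2/6 = 33.3% fails, the dose passes with at most 1 DLT in six: q⁶ + 6pq⁵. At p = 0.2: 0.262 + 0.393 = 0.655.
- *3(f) rule.* None in three escalates. One in three adds three men, all of whom must be free of DLT, because 2/6 reaches 33%: q³ + 3pq²·q³ = q³ + 3pq⁵. At p = 0.2: 0.512 + 0.197 = 0.709.

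| True DLT risk | 0.1 | 0.2 | 0.3 | 0.4 | 0.5 |
|---|---|---|---|---|---|
| Printed | 0.96 | 0.87 | 0.69 | 0.50 | 0.31 |
| 3(c) rule | 0.886 | 0.655 | 0.420 | 0.233 | 0.109 |
| 3(f) rule | 0.906 | 0.709 | 0.494 | 0.309 | 0.172 |
| Printed − 3(c), points | 7.4 | 21.5 | 27.0 | 26.7 | 20.1 |
| Printed − 3(f), points | 5.4 | 16.1 | 19.6 | 19.1 | 13.8 |

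Neither rule reproduces any cell.

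**2. What comes close.** Let 2 of 6 pass.

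- 3(f) flow: q³ + 3pq²(q³ + 3pq²) = 0.965 / 0.856 / 0.689 / 0.496 / 0.313, within 1.4 points of print. To two decimals it matches the last three cells; the first two would be 0.97 and 0.86.
- 3(c) flow: q³(1 − p³) + 3pq²(q³ + 3pq²) = 0.964 / 0.852 / 0.679 / 0.482 / 0.297, within 1.8 points.

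Both need 2/6 to be acceptable, which the under-33% requirement in 3(c) rules out.

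**3. One DLT in three.** Its probability is 3pq². If it closes the dose, the passing paths through it, 3pq⁵, are lost under either rule.

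| True DLT risk | 0.1 | 0.2 | 0.3 | 0.4 | 0.5 |
|---|---|---|---|---|---|
| Exactly 1 of 3 | 0.243 | 0.384 | 0.441 | 0.432 | 0.375 |
| 3(c) rule, closing at 1/3: q⁶ + 3pq⁵ | 0.709 | 0.459 | 0.269 | 0.140 | 0.063 |
| 3(f) rule, closing at 1/3: q³ | 0.729 | 0.512 | 0.343 | 0.216 | 0.125 |
| Loss, points | 17.7 | 19.7 | 15.1 | 9.3 | 4.7 |

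The loss peaks at p = 1/6: 3 × (1/6) × (5/6)⁵ = 0.201. At 75 Gy the 3(c) formulas apply with p as the risk at that dose; they then give the chance that 75 Gy, once reached, is declared the MTD.

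**4. None in three.** The rules differ on paths with none in the first three and two or more in the next three: q³(3p²q + p³) = 2.0 / 5.3 / 7.4 / 7.6 / 6.3 points.

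**5. First-subject stop.** The documents give no rate for these events. Suppose a share g of first-subject DLTs triggers the stop (assumption). The loss is then g·p·q⁵ under either rule. The 3(c) row becomes 0.871 / 0.639 / 0.408 / 0.226 / 0.105 at g = 25% and 0.856 / 0.623 / 0.395 / 0.218 / 0.102 at g = 50%. The stop can only widen the gap to the table.

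**The case against.** The strongest reply is that the intent is clear. Section 3(c) stops at two of three and adds men at one of three. Closing at one of three would leave the add-three instruction with nothing to act on. The general 33% rules name no review point and can be read as verdicts after six subjects, and the 60 Gy sentence in 3(f) does not tie its 33% to the first three men. On that reading, the losses in step 3 price a rule that nobody meant to apply.

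Most of this is fair. Counts do look intended, and those losses are the cost of a literal reading, not a forecast. But the reply does not reach the 75 Gy sentence, which applies the limit expressly to the first three men and so contradicts itself. Nor does inferred intent in one section cancel a stopping rule in another, when the protocol requires conduct exactly as approved.

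On none in three, 3(c) may be the outlier, since its own minimum-of-three paragraph sits better with 3(f). That shows the question is open; it does not settle it. The disagreement is explicit at 60 Gy only.

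On the table, it is true that it triggers no decision and that one boundary, 2 of 6, explains nearly all of its distance from 3(f). The SAP's strict inequality could tolerate 2 of 6 if 33% means one third, but the protocol's could not.

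**Conclusion.** The concern holds on all three parts. The 75 Gy sentence in 3(f) gives opposite orders at one DLT in three, a result expected in 24% to 44% of three-man cohorts over the tabulated risks. Sections 3(c) and 3(f) disagree after none in three at 60 Gy, worth 2.0 to 7.6 points of escalation probability. The printed table overstates escalation by 7.4 to 27.0 points against 3(c) and by 5.4 to 19.6 points against 3(f). Reading one in three as closure would err toward stopping early.

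The figures assume independent subjects with constant risk, and leave out the first-subject stop except where shown. The textual conflicts depend on no assumption. This should be corrected. A likely intent can be inferred for one in three, but not for none in three, and the table is wrong under either section as written.

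**What to change.** In 3(f), the Stopping Rules and the SAP's Primary Outcome section, replace every percentage with DLT counts that include subject 1:

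- **After subject 1:** only the stop in 3(c) for Grade 4 or higher events or death applies.
- **After 3 evaluable subjects:** 2 or more DLTs stop the dose; 1 adds three men; 0 has one stated action for each dose.
- **After 6:** 0 or 1 passes the dose; 2 or more fails it.
- **If a dose fails:** at 60 Gy the trial closes; at 75 Gy enrolment at that dose ends and 60 Gy is the MTD, as 3(c) has it.

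For none in three, choose between adding three men (3(c)) and escalating (3(f), possible at 60 Gy only). Adding three is the more cautious choice: it catches the cohorts with none in the first three and two or more in the next. Under the other branch, 60 Gy could be named the MTD on three men. Align the minimum-of-three paragraph of 3(c) with the choice, and delete the word in its opening that seems to leave out subject 1.

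Replace the table with 0.886 / 0.655 / 0.420 / 0.233 / 0.109 if 3(c) governs, or 0.906 / 0.709 / 0.494 / 0.309 / 0.172 if 3(f) governs, noting that both are before the first-subject stop. If the sponsor does want 2 of 6 to pass, the rule itself must say so.

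The cost is protocol and SAP wording and a short recalculation. The maximum of 12 is unchanged. Compared with 3(f), keeping the 3(c) branch costs three more men at 60 Gy and at least one more DLT window of 42 + 35 + 90 = 167 days, about 24 weeks.
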